Maximum Age

Aged nervous systems are known to be less-plastic and may not respond to neuromodulatory therapies as well as younger nervous systems. To reduce the possible effects of aging on the effectiveness of this pilot intervention we will limit enrollment to participants between 35 and 80 years of age (adult to aged groups defined by Geifman, Cohen, and Rubin (2013)).

References

INCLUSION OF WOMEN AND MINORITIES

All eligible subjects of both sexes and all minorities will be encouraged to participate in the proposed non-invasive brain stimulation treatment for post-stroke fatigue. Study participants will be recruited from the South Carolina Lowcountry tri-county area, which comprises Berkeley, Charleston, and Dorchester counties. The 2020 US Census¹ reported a population of approximately 800k individuals in the tri-county area with women making up 51.3% of the population. The racial and ethnic composition of the counties was White (69.2%), Black (25.7%), Hispanic (5.9%), Two or More Races (2.3%), Asian (2.1%), American Indian & Alaska Native (< 1%), and Native Hawaiian & Other Pacific Islander (< 1%). Women are reported to be approximately 53.5% of new and recurrent strokes². As this number is similar to the population we will use the population statistic for our recruitment, especially as our recruitment is of only 24 individuals.

We will monitor the diversity of the sample on a monthly basis and if recruitment target(s) are not adequate, we will take appropriate measures to improve diversity in recruitment.

Specific Plans for Maximizing Inclusion of Women and Minorities

Inclusion of Women: Inclusion or exclusion of participants will not differ based on sex and we aim to recruit similar numbers of males and females.

Inclusion of Minorities: Inclusion or exclusion of participants will not differ based on race/ethnicity. Based on the available literature on barriers to minority participation in clinical studies, we also will take the following additional steps to ensure representative enrollment of minority groups:

1. Emphasize that the goal is to recruit patients regardless of race or ethnicity. To assuage common suspicions that a specific race or ethnicity is being targeted,³⁻⁵ we will make clear to potential participants and their parents/guardians that patients of all races and ethnicities are being recruited.
2. Clearly explain that the purpose of informed consent is to protect, not relinquish, participants' rights. In several studies on the barriers to minority participation in clinical studies, participants have reported that they perceive the process of written, informed consent as relinquishing, rather than protecting, their rights.⁶⁻⁸ We will attempt to mitigate this source of distrust by explaining the intent of the informed consent process and emphasize the rights that the consent document enshrines.
3. Use straightforward and easy-to-understand language in consent forms. Participants' concerns about providing informed consent also relate to "not understanding technical legal and medical terminology"⁶ and "difficulty in fully understanding the complexities of research"⁶. We will attempt to mitigate this barrier to minority participation by taking extra care to write consent forms in easy-to-understand, straightforward language.

References

1. US Census Bureau, www.census.gov, Accessed 28 Feb 2022
2. Virani, S. S., Alonso, A., Aparicio, ..., and Tsao, C. W. (2021). Heart Disease and Stroke Statistics - 2021 Update: A Report From the American Heart Association. *Circulation*, 143(8), e254-e743.

RECRUITMENT AND RETENTION PLAN

Recruitment of Participants

Prospective participants will be recruited from multiple sources including RESTORE, ClinicalTrials.gov, and advertisements placed throughout the community (e.g. flyers posted in community centers and electronic flyers posted on social media sites). RESTORE is a bioinformatics-enabled database that contains over 1100 stroke survivors that have consented to be contacted for participation in research studies. This database is maintained by the NIH Center Of Biomedical Research Excellence (COBRE) for Stroke Recovery at the Medical University of South Carolina.

Research staff will search RESTORE for potential research participants and make initial contact via phone. Research staff will also respond to inquiries received from the community via phone. The research activities will be explained to prospective participants by the research staff. If the prospective participants express interest in partaking in the study they will be invited to the laboratory to confirm eligibility and provide written consent.

Retention

Enrolled participants will receive \$100 USD as remuneration for their participation in the proposed study. Remuneration will be delivered by pre-paid debit-type card that will be loaded at pre-determined milestones (after initial MRI, after each (5) treatment visit, after follow-up phone calls.

RISKS TO HUMAN PARTICIPANTS

[name] (PI) will be performing the proposed intervention at the College of Health Professions Research building on the Medical University of South Carolina campus. The research building is staffed with licensed clinical professions, physical and occupational therapists, and all research staff are trained in emergency procedures. Research staff also have basic life support (BLS) training from the American Red Cross, or equivalent. All investigators and research staff have completed computer-based CITI Human Subjects Research ethical and safety training, as required by the Medical University of South Carolina and the associated IRB. All research activity, informed consents, and continuing reviews will be reviewed by MUSC's IRB, before the research is started and continuing reviews will occur annually. The research staff will ensure that all information needed for the continuing reviews are available to the IRB in accordance with the IRB's requirements.

Human Subjects Involvement and Characteristics and Design

A total of 24 adults, between 35 and 80 years of age, with unilateral strokes more than 6 months post event will be recruited and enrolled over a one year period. The proposed randomized, single-blind, sham-controlled, trial will investigate the effects of anodal transcranial direct current stimulation (tDCS) on post-stroke fatigue and markers of inflammation. Participants will be randomly assigned to the active a-tDCS or sham group. Clinical and inflammatory markers will be assessed pre and post five consecutive days of a-tDCS applied to the motor cortex.

The inclusion/exclusion criteria for the study are as follows:

Inclusion Criteria:

1. Men and Women, any race or ethnicity, ages 35-80 years
2. 6+ months post-stroke
3. Average Fatigue Severity Score (FSS) ≥ 4 (indicates clinically significant fatigue)
4. Self-reports persistent fatigue for at least the past 6 months
5. Able to walk 10m unassisted

Exclusion Criteria:

1. Absolute contraindications to MRI, TMS, tDCS
2. Inability to follow 3-step instructions
3. Multiple strokes on opposite hemispheres
4. Diagnosis of comorbid neurological conditions (e.g. multiple sclerosis, Parkinson's disease, and dementia)
5. Severe hypertension (resting SBP > 200 mmHg or DBP > 120)
6. Cerebellar or brainstem strokes
7. Hospital Anxiety and Depression Scale (HADS) score > 7 , depression or anxiety
8. Pregnancy

Study Procedures, Materials, and Potential Risks

Source of Materials

Data will be in the form of structured interviews, self-reported rating scales and questionnaires, surface electromyography recorded transcranial magnetic (TMS) evoked potentials, and MRIs. No identifiable information is expected to be collected outside of the consent process. Once consented individuals will be assigned a non-identifiable research ID number that will be used to mark/track collected data.

Research Procedures and Potential Risks

Although unlikely, it is possible that some participants may experience distress when asked questions pertaining to their feelings of fatigue, depression, anxiety, or pain. Some participants may also experience

distress during MRI sessions or TMS assessments. However, previous and ongoing research by our research group indicates that these risks are minimal.

Specific risks, which are all low/minimal, associated with the research procedures are as follows:

tDCS: Commonly reported side effects are as follows: local skin irritation with light itching/tingling/ burning, mild headache, or nausea. There have also been rare cases of mild burns at the procedure site.

TMS: There is a very low risk of a seizure after TMS. The risk of seizure induction by this protocol has been thoroughly assessed and the TMS parameters have been chosen to be well within published safety guidelines for the conduct of TMS studies in human subjects.

Blood Draw / Venipuncture: Risks associated with blood draws include momentary discomfort and/or bruising. Infection, excess bleeding, clotting, or fainting is possible, although unlikely.

MRI: There have been no ill effects reported from exposure to the magnetism or radio waves used in this test. A known risk is that the magnet could attract certain kinds of metal. Therefore, we will perform a detailed screening, provided by the Center for Biomedical Imaging (CBI), before any participants are imaged.

Walking Tests: Some of the activities performed during this study will be performed while the participants are walking or standing. During these activities, participants may lose their balance or become unsteady.

Pregnancy: We do not know if the study intervention will affect mother's milk or an unborn fetus. Therefore, breast-feeding and pregnant women are not allowed to take part in the study. If a potential participant is pregnant or become pregnant they will be removed from the study as there may be risks to the embryo or fetus that are unknown at this time.

Randomization: The treatment you receive may prove to be less effective or to have more side effects than the other study treatment(s) or other available treatments.

Loss of Confidentiality: There is a risk of loss of confidentiality or personal health information. We will collect the participants age, date of stroke, sex, and racial/ethnicity to classify our sample and for use as influencing factors on intervention effectiveness.

Unknown Risks: The experimental treatments may have unknown side effects. The researchers will let you know if they learn anything during the course of the study that might make you change your mind about participating in the study.

Adequacy of Protection Against Risks

Informed Consent Procedures

All personnel are trained in the responsible conduct of human research. Informed consent will be collected by the on-site study coordinators ([name], [name]) or the PI ([name]). All study personnel will be familiar with the treatment protocol. This will ensure each person collecting informed consent is familiar with all aspects of the study. Individuals obtaining informed consent will role-play the consent procedures with the PI until they demonstrate competency.

Written/signed informed consent will be collected in a private and interruption-free room inside the study offices inside the College of Health Professions Research building. Potential candidates will not be required to decide to participate at this initial visit, though that possibility will be available. If potential participants wish to discuss participation with their families and/or significant others, or other healthcare providers they will be encouraged to do so. The informed consent document will outline, a) the sponsorship of the study; b) the nature, purpose, and procedures of the research study; c) the voluntary nature of participation (i.e., participation is not required, participation can be discontinued at any time); d) the duration of the study; e) potential risk and discomforts, as

well as benefits of participating; f) that all information will be kept confidential subject to the provisions of state and federal law; and g) compensation. Participants will be informed that they can discontinue their participation in the study at any time and that this decision will not influence future healthcare or research participation at MUSC. Private information collected as part of the informed consent process is the participants full name and signature.

Protections Against Risk

Specific mitigation plans for each of the known risks are provided below:

tDCS: To reduce the chance for an adverse event (AE)/reaction electrode preparation and contact will be constantly checked. Research staff will also engage with the participants during intervention application and monitor the participants' physiological and emotional state. Our research group has performed over 100 tDCS sessions with no adverse or serious adverse events.

TMS: To minimize risk, we will be using single- and paired-pulse TMS, as the majority of adverse events in the literature have occurred after repetitive TMS and we will follow published safety guidelines. Individuals with a history of seizures, you will not be allowed to participate in this portion of the study. Participants will undergo IRB approved screening prior to enrollment.

Blood Draw / Venipuncture: To reduce venipuncture risks, all procedures will be performed by licensed nursing staff at the South Carolina Clinical and Translational Research Institute on the medical campus.

MRI: We will perform a detailed screening, provided by the Center for Biomedical Imaging (CBI), before any participants are imaged. If there is any question about potentially hazardous metal within a participant's body, they will be excluded from participation in this research study. We will also keep the examining room locked so that no one carrying metal objects can enter while participants are in the scanner.

Walking Tests: To ensure that participants do not fall they will wear a safety harness that is attached to the ceiling. The harness will prevent participants from hitting the ground in the event they lose their balance or become unsteady.

Pregnancy: All prospective participants of childbearing potential will be required to undergo urinalysis to determine pregnancy status.

Loss of Confidentiality: To minimize this risk, we will use a non-identifiable research id number to label all collected data. Any data collected on physical media will be stored in locked file cabinets where only authorized research personnel have access. Electronically collected data will be stored on secured password protected IT network resources.

Potential Benefits of the Proposed Research

Post-stroke fatigue is well known but poorly understood phenomenon that significantly contributes to a poorer quality of life. The proposed research has the potential to reduce the impact of post-stroke fatigue leading to improvements in physical, cognitive, and emotional health. The potential benefit of improving function and quality of life in individuals with post-stroke fatigue outweigh the minimal risks associated with the study's procedures.

Importance of the Knowledge to be Gained

Another benefit of this proposal is the possibility of improving our knowledge of the inflammatory contributions to post-stroke fatigue. Increasing our mechanistic knowledge may guide future refinement and development of treatments for post-stroke fatigue. As stated, the risks associated with the proposed research are minimal leading to a favorable cost-benefit analysis.

DATA SAFETY AND MONITORING PLAN

This section is based on the recommendations in NIDA's "Guidelines for Developing a Data and Safety Monitoring Plan" (www.drugabuse.gov/funding/dsmbssop.html).

Summary of the Protocol

The intervention being studied is a five-session anodal transcranial direct current stimulation (tDCS) intervention delivered over five consecutive days. Measures of post-stroke fatigue and inflammation (central inflammation measured by magnetic resonance spectroscopy and peripheral markers measured via blood analysis) will be made before and after the intervention.

Trial Management. The study will be primarily managed from the Functional Neurostimulation Laboratory ([name], PI) within the Division of Physical Therapy within the College of Health Professions at the Medical University of South Carolina. The target population is adults more than six months post-stroke with clinically present fatigue (average Fatigue Severity Scale > 4).

Data Management and Analysis

The primary outcome of the study is the change in post-stroke fatigue severity (fatigue severity scale (FSS), pre- and post-intervention) and markers of central (measured using magnetic resonance spectroscopy (MRS)) and peripheral (measured via blood analysis) inflammatory markers. Analyses will be guided by the specific hypotheses of the study. Post-hoc exploratory analyses will be conducted with two-tailed tests and more conservative statistical procedures which guard against Type I error (e.g., Tukey tests). All primary hypotheses will be tested at level of significance $\alpha=0.05$. We will also estimate the effect sizes of interest and provide 95% confidence intervals for them.

Quality Assurance

Data quality will be monitored by random inspection of the completed forms by research staff/PI.

Regulatory Issues. All unexpected Adverse Events (AEs) will be reported to the MUSC IRB within 10 working days. Serious AEs (SAEs) will be reported within 24-business hours. Follow-up of all unexpected and serious AEs will also be reported to the IRB. All AEs will be reviewed weekly by the PI and yearly by the IRB. Any significant actions taken by the local IRB and protocol changes will be relayed to NIH. AEs and SAEs occurring during the course of the trial will be collected, documented, and reported in accordance with IRB requirements.

Definition of AE and SAE

Adverse events are defined as any untoward medical occurrence that may present itself during treatment or administration of an intervention, and which may or may not have a causal relationship with the treatment.

Serious adverse events are defined as any medical occurrence that:

- Results in death,
- Is life-threatening,
- Requires inpatient hospitalization or prolongation of existing hospitalization,
- Results in persistent or significant disability/incapacity,
- Is a congenital anomaly/birth defect. OR
- Requires intervention to prevent one of the above outcomes.

Documentation and Reporting

AEs/SAEs will be documented and reported as per IRB requirements. Research staff will identify adverse events and obtain all available information to assess severity, seriousness, study relatedness, expectedness, outcome, and the need for change or discontinuation in the study intervention. Adverse events will generally be documented on AE Logs and AE Case Report Forms (CRFs). Additional relevant AE information, if available, will be documented in a progress note in the research record as appropriate to allow monitoring and evaluating

of the AE. If the AE meets the definition for serious, appropriate SAE protocol specific reporting forms will be completed and disseminated to the appropriate persons and within the designated timeframes as indicated above. For each AE/SAE recorded, the research staff will follow the AE/SAE until resolution, stabilization or until the subject is no longer in the.

When a reportable SAE is identified, the PI and/or Study Coordinator will initiate an SAE form, and the following individuals will be notified by facsimile transmission, email and/or telephone within 24-business hours of the initial notification of the SAE:

- i. The PI and laboratory clinical staff will provide oversight, consultation, assessment, and documentation as appropriate of the SAE.
- ii. The research staff will notify the MUSC IRB and complete the AE report form in conjunction with the PI. The MUSC IRB meets monthly and is located at [name]. Communication with the IRB is through email, memos, official IRB forms, and online reporting.
- iii. The NIH program officer.

If complete information is not available when the initial 24-hour SAE report is disseminated, follow-up information will be gathered to enable a complete assessment and outcome of the event. This information may include hospital discharge records, autopsy reports, clinic records, etc. The research staff will attach copies of source documents to the SAE report for review by the PIs and for forwarding to the NIH program officer as appropriate within 2 weeks of the initial SAE report. In addition, the PIs will provide a signed, dated SAE summary report, which will be sent to the NIH Medical Safety Officer within two weeks of the initial SAE report.

We will report adverse events to the MUSC IRB online as soon as possible, but no later than 10 working days after the investigators first learns of the event. The MUSC IRB AE reporting requirements are as follows: All deaths that occur during the study or 30 days post termination from the study are required to be reported as adverse events even if they are expected or unrelated. Other adverse events are reportable to the MUSC IRB if the AE is unexpected AND related or possibly related AND serious or more prevalent than expected. All three criteria must be met for an AE to be reported to the MUSC IRB. The IRB definition of unexpected is that the AE is not identified in nature, severity or frequency in the current protocol, informed consent, investigator brochure or with other current risk information. The definition of related is that there is a reasonable possibility that the adverse event may have been caused by the device or intervention. Reportable AEs are reviewed by the IRB Chair and reported to the IRB Board at the next meeting.

Trial Safety

The potential risks and benefits and methods to minimize these risks are outlined in Section 3.1, Protection of Human Subjects Section. Protocols for reported AEs and SAEs are outlined above. All unexpected AE and SAEs will be monitored until resolved. A detailed summary of all AEs will be prepared weekly by the research staff and relayed to the PI. Study procedures will follow as much as possible the FDA's Good Clinical Practice Guidelines (www.fda.gov/oc/gcp). All requests by subject's physicians and other medical providers will be referred directly to PI.

DSMP Administration

The PI will be responsible for ensuring participants' safety on a daily basis.

The PI will examine the database for missing data, unexpected distributions or responses, and outliers. We will report results at the end of the trial.

DSM Board

A DMSB is not required as the intervention is considered minimal risk and the minimal duration of the trial.

Confidentiality will be maintained during all phases of the trial including monitoring, preparation of interim results, review, and response to monitoring recommendations.

Protocol version 2

Date: 28 Mar 2022

ClinicalTrials.gov Requirements

In accordance with Public Law 110-85, the proposed trial will be registered with ClinicalTrials.gov. Applicable requirements regarding results reporting will be adhered to.

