
[figure not shown]

Figure 2: Research protocol timeline. Three additional followup phone-calls to assess fatigue will be performed 1, 2, and 4 weeks post the participants' last tDCS treatment.

full list of questionnaires and clinical measures is presented in Table 1. *The primary outcome for this study is trait fatigue measured by the FSS.*

Study Design and a-tDCS Treatment

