This pilot proposal is a randomized longitudinal single-blind sham-controlled intervention. Individuals with PSF will be randomly assigned to the sham or a-tDCS treatment group. Before and after five consecutive days of a-tDCS applied bilaterally over the left and right lower extremity motor cortex, PSF and nervous system and peripheral inflammation will be measured, similar to De Doncker et al. (2021). The tDCS treatment will consist of twenty minutes of 4 mA a-tDCS delivered via two carbon rubber electrodes placed inside sponge pads (1x1 tDCS, Soterix, USA). The current will be ramped up 4 mA over 30 seconds. Each electrode has a surface area of 70 cm², resulting in a current density of 0.06 mA/cm² and a charge density of 1.1 C/cm², which are within current safety guidelines (Bikson et al. 2016). The anode electrode will be centered on the interhemispheric fissure and the central sulcus. This area was chosen due to its previous use in fatigue studies using neuromodulation (multiple sclerosis, Ferrucci et al. 2014; fibromyalgia, Altas et al. 2019; Stroke, De Doncker et al. 2021). The motor cortex is being used more often in neuromodulation studies due to its structural and functional connectivity to cortical and subcortical networks/nodes, e.g. basal ganglia, cingulate cortex. The cathodal electrode will be placed on the nonparetic shoulder. Modeling of cephalic and extracephalic tDCS montages indicates that extracephalic placement of the cathode leads to deeper current flow in the somatosensory cortex (Noetscher et al. 2014). The sham tDCS procedure will be performed in the same manner as active a-tDCS, however, the current will be ramped up and down over 30 seconds (Fridricksson et al. 2018). Figure 2 displays the protocol timeline. Days 2-6 will be consecutive, no more than 36 hours will be allowed between treatment visits. If more than 36 hours elapses the participant will be withdrawn from the study. The measurement of state fatigue, via f-VAS, will be performed before and after each tDCS treatment visit. Follow-up assessments of state and trait fatigue will be performed via phone at one (Follow-up 1), two (Follow-up 2), and four weeks post-treatment (Follow-up 3). The primary study outcome will be the comparison of the FSS scores obtain at baseline (Visit 1) and one week post-tDCS (Follow-up 1).

Neuroimaging

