
Table 1: Clinical Outcome Measures

Domain	Instrument
Fatigue (State)	Visual Analogue Scale
Fatigue (Trait)	* Fatigue Severity Scale (FSS) (Krupp et al. 1989) Modified Fatigue Impact Scale (mFIS) (Fisk et al. 1994) Fatigue Assessment Scale (FAS) (Michielsen et al. 2003)
Anxiety	Hospital Anxiety and Depression Scale (Zigmond and Snaith 1983)
Depression	Patient Health Questionnaire 9 (PHQ-9) (Spitzer and Williams 1999)
Pain	Defense and Veterans Pain Rating Scale (DVPRS) (Polomano et al. 2016)
Physical Function / Mobility	10 m walk over GAITRite (Kindred et al. 2019)
Community Participation / Quality of Life	Standard Form 36 (Anderson et al. 1996)

* Primary outcome measure for Aim 1

Statistical Analysis

Aim 1 Hypothesis: Five days of a-tDCS applied to the lower extremity motor cortex will result in a reduction of PSF severity in individuals with chronic stroke. A two-factor, between-subjects factor of GROUP (active a-tDCS, sham) and within-subjects factor of TIMEPOINT (pre, post), mixed model ANOVA will be used to test this hypothesis. The primary outcome variable for this analysis is the FSS scores. We will also calculate measures of effect size to power future studies.

Aim 2 Hypothesis: Five days of a-tDCS applied to the lower extremity motor cortex will result in a reduction of inflammatory markers within the central nervous system and the peripheral blood. Pre- and post-intervention markers of inflammation will be compared using a mixed model, two-factor ((between-subjects factor of GROUP (active a-tDCS, sham) and within-subjects factor of TIMEPOINT (pre, post)), ANOVA. Each outcome measure (MI, tCR, IL-1, TNF- α , etc) will be tested independently.

Additional Analyses: Examine the possible relationship between PSF severity and inflammatory markers. This relationship may provide mechanistic insight into the effect of tDCS on PSF and allow us to possibly predict future responders/non-responders to a-tDCS treatments of PSF. Pearson's correlations will be calculated between baseline measures of inflammation and FSS scores to determine a possible role of current state inflammation on PSF severity. Correlations between the change in FSS scores and inflammation, pre- and post-a-tDCS, will be calculated to provide preliminary evidence of a possible mechanism of reduced inflammation and improved PSF.

Potential Problems / Solutions

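### The analysis section adds the MRS and blood markers to a primary outcome that the design sections define as the FSS alone, and no success rule is stated

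*Combined protocol and SAP*

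**What the plan says.** Three statements define the primary outcome of the study as a whole.

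- End of Recruitment and Consent: "The primary outcome for this study is trait fatigue measured by the FSS".
- Study Design and a-tDCS Treatment: "The primary study outcome will be the comparison of the FSS scores obtain at baseline (Visit 1) and one week post-tDCS (Follow-up 1".
- Data Management and Analysis, inside the data safety and monitoring plan: "The primary outcome of the study is the change in post-stroke fatigue severity (fatigue severity scale (FSS), pre- and post-intervention) and markers" of central inflammation (by MRS) and peripheral inflammation (by blood analysis).

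The last of these sections also says "All primary hypotheses will be tested at level of significance" 0.05, with no split, ordering or adjustment. Its only protection against Type I error is for other analyses: "Post-hoc exploratory analyses will be conducted with two-tailed tests and more conservative statistical procedures which guard against Type I error".

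Table 1 stars the FSS with the footnote "Primary outcome measure for Aim 1". Statistical Analysis gives the FSS a hypothesis under Aim 1 and the markers a separate one under Aim 2, where the list of marker outcomes ends "etc) will be tested independently". Biostatistical Justification sizes the trial on the FSS alone.

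**The concern.** Two of the study-level statements admit one outcome. The third admits a family of outcomes whose members are not listed. If the FSS shows no effect and one metabolite or cytokine reaches p < 0.05, the third statement lets that marker be reported as a primary result and the first two do not. Two careful readers could therefore disagree on whether the trial met its primary outcome.

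The room for choice is wide. The imaging and blood sections list three metabolites, their ratios to NAA, four voxels and five blood markers, in a 24-person pilot with no sample-size basis for any of them. The plan also commits to ClinicalTrials.gov registration and results reporting, which need one definition.

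**Working it through.** **1. The statements side by side**

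| Section | Primary outcome | Timing | Level |
|---|---|---|---|
| Recruitment and Consent | FSS | not given | study |
| Study Design and a-tDCS Treatment | FSS | Visit 1 vs Follow-up 1 | study |
| Table 1 footnote | FSS | not given | Aim 1 only |
| Statistical Analysis, Aim 1 | FSS | pre, post | Aim 1 only |
| Data Management and Analysis | FSS, MRS markers, blood markers | pre and post intervention | study |

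The first two rows and the last row are all at study level, so they cannot all be true.

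**2. Does anything resolve it?**

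- The Table 1 footnote allows one primary per aim. But it names none for Aim 2, does not rank the aims, and would not fit an FSS-only study primary.
- "Analyses will be guided by the specific hypotheses of the study" leads back to Statistical Analysis, which contains both aims.
- Testing each marker independently describes single tests. It does not say which results make the trial positive.
- The sample size supports an FSS-only intent but does not amend the other sentence.

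**3. The plan's own figure**

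Biostatistical Justification gives 8 per group for 0.45 FSS points, 80% power and alpha 0.05. No SD is given, so the figure cannot be reproduced directly. Solved backwards with a two-sided t-test on change scores, 8 per group needs a standardised effect of 1.507, hence a change-score SD of 0.45 / 1.507 = 0.299. What matters here is only that no marker enters the calculation.

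**4. How many tests could be primary (assumed, since the plan does not list them)**

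- 2: one per aim.
- 3: FSS, one central marker, one peripheral marker.
- 9: FSS + 3 metabolites in one combined region + 5 blood markers.
- 30: FSS + (3 metabolites + 3 ratios) × 4 voxels + 5 blood markers = 1 + 24 + 5.

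**5. False-positive rate if any one success counts (assumed rule)**

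For k independent tests the rate is 1 − 0.95^k. For correlated tests it was simulated: 12 per arm, two-sided t-test on change scores (equivalent to the group-by-time interaction), equal correlation between outcomes, no true effects, 60,000 runs.

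| Tests | Correlation 0 (formula) | 0.5 | 0.8 | 0.8, with 8 per arm |
|---|---|---|---|---|
| 2 | 0.0975 | 0.092 | 0.079 | 0.081 |
| 3 | 0.143 | 0.126 | 0.098 | 0.103 |
| 9 | 0.370 | 0.276 | 0.170 | 0.174 |
| 30 | 0.785 | 0.524 | 0.267 | 0.277 |

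Under the FSS-only reading the rate is 0.05.

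**6. If all had to succeed (the opposite rule)**

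The false-positive rate cannot exceed 0.05 for any number of tests. At correlation 0.8 and 12 per arm it was 0.020, 0.013 and 0.004 for 2, 3 and 9 tests. The cost falls on power: at an assumed 80% per test and independence, joint power is 0.8^9 = 0.134 for 9 tests and 0.8^30 = 0.001 for 30.

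**The case against.** The strongest reply is that one stray sentence in a monitoring plan is being set against the body of the protocol. The design text names the FSS twice, once with timing. The Aim 1 analysis calls the FSS its primary variable. No marker is called primary in Statistical Analysis, and the sample size rests on the FSS. This is also a pilot meant to supply effect sizes for later studies, so an any-or-all success rule may never have been in view.

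Much of this stands as evidence of intent: the FSS-only reading is the better supported one. That favours the fix below but does not remove the conflict. The outlying sentence is current text, sits under the heading that covers analysis, and is followed by a commitment to formal testing at 0.05.

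The error rates are also open to challenge. They span at most 5% to 79%, depending on assumptions. The 2- and 3-test counts do not match the plan to test each marker separately, and the 9-test count pools regions and drops the NAA ratios. Only 30 follows the full list. This is fair: the figures are illustrative, and the finding does not rest on them.

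Finally, the investigator could keep markers as primary by listing them, stating the rule and dividing alpha. That is legitimate, but a Bonferroni division would put each test at 0.05 / 9 = 0.0056 or 0.05 / 30 = 0.0017 in a trial sized for one test at 0.05.

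**Conclusion.** The concern holds and must be fixed. The protocol carries two incompatible definitions of the study's primary outcome, with nothing to say which governs and no rule for success across several outcomes. That conclusion rests on the text alone.

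The size of the error depends on a rule the plan does not write. If any one success counts, the chance of a false-positive primary result rises from 5% to about 8% to 10% (2 tests), 10% to 14% (3), 17% to 37% (9) or 27% to 79% (30), as correlation falls from 0.8 to 0. If all must succeed, it stays at or below 5%. Test counts, correlations and the rule are assumptions. Dropping to 8 completers per arm barely changes the figures at correlation 0.8.

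The timing is a smaller matter of wording. The pre/post labels in Statistical Analysis and in Data Management and Analysis do not name the Visit 1 to Follow-up 1 comparison, but they do not contradict it.

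**What to change.** In Data Management and Analysis:

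- Name the FSS change from Visit 1 to Follow-up 1 as the sole primary outcome, tested at two-sided 0.05. The planned interaction F test is already non-directional, so stating the sidedness changes nothing in the analysis.
- Label all MRS and blood markers secondary or exploratory, reported with effect sizes and the 95% confidence intervals that section already promises.
- State that no single nominally significant marker counts as a positive primary result.

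In Statistical Analysis, define the Aim 1 time factor as Visit 1 and Follow-up 1, so that it matches the design section.

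This takes a few sentences in two sections. Data collection, sample size and the planned ANOVA stay as they are. The price is that a marker finding can no longer be presented as a primary result.
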